14.5.2 FORMULATION, APPEARANCE, PACKAGING, AND LABELING

Melatonin is a small molecule hormone with the chemical name of N-[2-(5-methoxy-1H-indol-3-yl)ethyl] and whose preparation is well characterized. It will be a capsule.

The placebo will be encapsulated to look similar to the melatonin capsule, but it will not contain the active ingredient.

Melatonin and the placebo capsules will be packaged in high-density polyethylene bottles with a childresistant screw cap. All packaging will be labeled to indicate that the product is for investigational use.⁶⁰

14.5.3 DRUG DISPENSING, STORAGE, AND STABILITY

Unblinded study personnel will manage melatonin and placebo disbursement to maintain blinding among participants and blinded study personnel, including site investigators.

Melatonin and the placebo should be stored at 20 °C to 25 °C (68 °F to 77 °F) with excursions permitted between 15 °C to 30 °C (59 °F to 89 °F) and away from heat, moisture, and light. Neither product should be frozen.

14.5.4 DOSING AND ADMINISTRATION

Melatonin will be administered for 8 weeks. Melatonin dosing will be one capsule of 3 mg immediate release daily consumed 2 hours before the participant's scheduled bedtime, which is defined as the time at which the participant tries to fall asleep.

Placebo dosing will be one placebo capsule once daily consumed 2 hours before the participant's scheduled bedtime.

14.5.5 RATIONALE FOR SELECTION OF DOSE

The proposed dose has previously been shown to phase shift the biological clock^{67,68} and promote daily entrainment in blind individuals who cannot perceive light.⁶⁹ Other studies have shown that oral melatonin can help minimize jet lag symptoms.^{70,71}

14.6 RESET-PASC INFORMATION

RESET-PASC will involve providing participants with education on healthy sleep behaviors through short videos (and/or paper brochures); a tailored prescription for timing of bedtime, light and melatonin/ placebo use; and electronic messages to reinforce sleep timing. Educational videos will be accessed by the participant at the beginning of the intervention period. A central investigator will review each participant's survey data remotely and will develop an initial prescription for when the participant should be exposed to the tailored light/sham light, when he/she should take melatonin/placebo, and when the participant should go to bed. This prescription will be communicated to the participant during a telephone call by a central investigator. After the initial "sleep prescription," the participant will be contacted by telephone or text message approximately every 2 weeks for 6 weeks to reinforce (or troubleshoot) light and drug/placebo adherence and bedtime routines. To inform recommendations, a central team will review responses from periodic electronically distributed questionnaires (SASS-Y, PGIC). The central team assessing the surveys will be blinded to the participant's intervention allocation.

14.7 EVENTS OF SPECIAL INTEREST

None

14.8 STATISTICAL CONSIDERATIONS (APPENDIX LEVEL)

14.8.1 RATIONALE FOR SELECTION OF DOSE

Complex PASC-related Sleep Disturbances is a 2X2 factorial design. There will be two independent primary endpoints, namely (1) PROMIS 8b SD and (2) variability in sleep onset. Thus, each endpoint will be tested at .025 type I error rate to maintain the overall error rate at .05. Similar assumptions as in Appendix A (Section 13.7.1) will be used to calculate the statistical power for PROMIS 8b SD endpoint, except using type I error rate at .025 level. A total of 560 participants is needed to detect a 5-unit difference between groups with at least 90% power. For the variability in sleep onset with type I error rate of .025, a total sample size of 600 participants is needed. The study will have at least 90% power to detect an effect size between .35 and .45, assuming variability in sleep onset of SD = 70 minutes in the control group and roughly SD = 45 minutes in the intervention group. Thus, this study will require a total of 600 participants to maintain at least 90% power for both primary endpoints.

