10.4.1 OVERALL STATISTICAL DESIGN

This study is a platform protocol designed to be flexible and consists of distinct symptoms of sleep disturbance using different interventional designs integrated into COVID-19 programs and subsequent treatment plans. For this study, data from all enrolled participants that receive the control intervention or treatment intervention will be included in the analyses. Between-group comparisons of the primary study endpoint, change from baseline in PROMIS SRI/SD T-scores (and sleep onset variability for Complex PASC-Related Sleep Disturbance), and clinically important secondary endpoints (eg, PROMIS 10a Fatigue, Neurocognitive Battery, etc.) will be analyzed using ANCOVA models. For endpoints that are categorized into binary secondary outcomes, logistic regression models will be utilized. Comparisons of the treatment groups for repeated measures outcomes over time will be investigated using mixed-

effect linear models with Generalized Estimating Equations (GEE) to account for correlated data withinparticipant.

Analyses of the primary endpoint measures, PROMIS SRI/SD T-scores (and sleep onset variability for Complex PASC-Related Sleep Disturbance), will require both the baseline and follow-up measurements. Participants missing one or both of their respective PROMIS SRI/SD measurements (or sleep onset variability) will not be included in the primary analysis cohort, ie, missing data on the primary endpoint will not be imputed in the primary analyses. However, sensitivity analyses will be conducted using imputation methods (eg, single or multiple imputation) to investigate the robustness of study findings. All testing hypotheses and estimated confidence intervals will be two-sided at a .05 significance level. The type I error rate of .05 for the secondary endpoints will be controlled using the Hochberg method.⁵⁰

Changes to the overall statistical design that occur prior to locking the study database will be detailed in the final SAP.

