10.4.3 ANALYSIS OF THE SECONDARY ENDPOINT(S)

The secondary endpoints listed below will be analyzed using ANCOVA linear regression models similar to the approach used in the primary endpoint:

- PROMIS 10a Fatigue total score
- Neurocognitive Battery total score
- ECog2 total score
- PASC Symptom Questionnaire total score
- ISI total score
- Sleep diary
 - Average nocturnal and 24-hour sleep duration and sleep efficiency
 - o Within-individual standard deviation of sleep onset
- Activity tracker
 - Within-individual standard deviation of sleep onset timing
 - o Average nocturnal and 24-hour sleep duration and efficiency

Comparisons of the treatment groups for endpoints with repeated measures outcomes over time will be investigated using mixed-effect linear models with GEE to account for correlated data within-participant.

If the null hypothesis is rejected for the primary outcome, then testing of the above secondary outcomes will be performed using the Hochberg method to control the type I error rate at 0.05. However, if the null hypothesis for the primary outcome is not rejected, then inferences on the secondary endpoints will be considered exploratory.

Safety endpoint. Safety endpoints include the proportion of participants who experience individual SAEs and the proportion who experience at least one or more SAEs. These will be analyzed in the safety population defined as the subset of mITT participants who confirm at least one administration of study intervention/control. Events of Special Interest (ESIs) will be summarized by the study intervention appendix and duration. The incidence of AEs/SAEs leading to discontinuation will also be summarized.

Other endpoints. Other secondary endpoints are either binary or continuous. Binary endpoints will be analyzed by logistic regression models to estimate the odds ratios [95% confidence intervals] between the treatment groups. Continuous endpoints will be analyzed using ANCOVA linear regression models.

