13.7 STATISTICAL CONSIDERATIONS (APPENDIX LEVEL)

13.7.1 SAMPLE SIZE DETERMINATION

An Analysis of Covariance (ANCOVA) linear regression model will be used to compare PROMIS-8a Tscores for the investigational intervention versus control at post-treatment measurement with an

adjustment for the baseline PROMIS-8a measurement. The key determinants of power include the number of participants (ie, sample size), the hypothesized difference in mean T-scores at follow-up for investigational intervention versus control among participants with similar baseline T-scores (ie, the treatment effect), and the standard error of the regression coefficient representing the mean difference in the ANCOVA model. A clinically meaningful treatment effect is assumed to be 5 T-score. The amount of statistical information about treatment effect (β_{trt}) can be quantified as $I = [Var(\hat{\beta}_{trt})]^{-1}$ which is the reciprocal of the estimated treatment effect variance in the primary analysis ANCOVA model. In order to detect a treatment effect of ($\beta_{trt} = 5$) with power $1 - \beta$ and two-sided type-I error α , the required amount of statistical information is given by I = { $(z_{\alpha/2} + z_{\beta})/5$ }² where $z_{\alpha/2}$ and z_{β} are the $(1 - \alpha/2)$ and $(1 - \beta)$ quantiles of the standard normal distribution. The sample size estimation is based on the rough approximation of $V(\hat{\beta}_{trt}) \approx \frac{4\sigma^2(1-R^2)}{n} \cong \frac{4\sigma^2}{n}$, when $R^2 \approx 0$, here σ^2 is the variance of PROMIS-8a T-scores within each treatment group, R^2 is the ANCOVA model's coefficient of determination, and n is the total sample size for active intervention plus control. If the estimated treatment effect is assumed to be 5 units, $\hat{\sigma} = 15$ units (ie, an effect size of .33), two-sided type I error of .05, thus the required total sample size for 90% power to detect a treatment effect of 5 T-score units is 379 participants. Accounting for a 20% attrition rate will lead to a total sample size of 474 participants, which is 237 participants per group (Figure 4).

Standard deviation

Figure 4. Sample Size Estimates Using the ANCOVA Model

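### Appendix B's fixed .025/.025 split between its two primary endpoints is valid, but it gives up power that a Holm step-down would keep at the same .05 and the same sample size.

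*Protocol*

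**What the plan says.** Protocol 14.8.1 sets the testing rule for the 2x2 factorial Appendix B. It names two primaries: "There will be two independent primary endpoints, namely (1) PROMIS 8b SD and (2) variability in sleep onset". It then fixes the level for each: "Thus, each endpoint will be tested at .025 type I error rate to maintain the overall error rate at .05". Protocol 10.4.1 makes all tests two-sided.

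The sample size is worked out one endpoint at a time. For PROMIS 8b SD the Appendix A assumptions "will be used to calculate the statistical power for PROMIS 8b SD endpoint, except using type I error rate at .025 level", with the result: "A total of 560 participants is needed to detect a 5-unit difference between groups with at least 90% power". Sleep onset variability is given 600 participants, for effect sizes between .35 and .45. The section closes: "Thus, this study will require a total of 600 participants to maintain at least 90% power for both primary endpoints".

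Neither 14.8.1 nor 10.4.1 to 10.4.3 passes alpha from one primary to the other. The only onward step is from the primary to the secondary endpoints. After the primary null is rejected, "testing of the above secondary outcomes will be performed using the Hochberg method to control the type I error rate at 0.05". That text speaks of one primary outcome and does not say whether one or both Appendix B primaries must succeed.

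**The concern.** A fixed .025/.025 split is plain Bonferroni. Suppose 8b SD succeeds at .025 and onset variability gives p = .03. The protocol calls the second primary a failure. Yet testing it at .05 once the first null has been rejected keeps the error over the two endpoints at .05, whatever their correlation.

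Section 14.1 wants the objective and the subjective measure taken together to characterize the effect on complex sleep disturbance. Winning on both is therefore a result of interest, and it is the one that loses most under the fixed split. The level is written into the protocol as a rule, so this is not a detail left open for the SAP.

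**Working it through.** **Inputs.** Two-sided .025 per endpoint, 90% power, a 5-unit difference and 600 in total come from 14.8.1 and 10.4.1. SD 15 (effect size .33) and 20% attrition come from 13.7.1. The onset effect size of .35 to .45 comes from 14.8.1. Three things are assumed: equal allocation, so that each intervention is compared half against half at the factorial margin; 20% attrition applied to the 600; and the correlation between the two test statistics.

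**The plan's own figure.** Total n = 4σ²(z₁ + z₂)²/δ², with z₁ = 2.2414 (two-sided .025) and z₂ = 1.2816 (90% power).
- 4 × 225 × 3.523² / 25 = 446.8, which rounds up to 224 per side, or 448.
- 448 / .80 = 560, exactly as stated. The 560 is thus an enrolled figure that includes 20% attrition.
- For onset variability at .35: 4 × 3.523² / .35² = 405.3, so 406 completers, or 508 enrolled. The planned 600 is more than enough.

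**Fixed split at 480 completers (600 × .80).**
- 8b SD: noncentrality 5√480/(2 × 15) = 3.651. Power at .025 is Φ(3.651 − 2.241) = .9207; at .05 it is Φ(3.651 − 1.960) = .9546.
- Onset variability at .35: noncentrality .35√480/2 = 3.834. Power at .025 is .9444; at .05 it is .9695.
- Both, at correlation 0: .9207 × .9444 = .8695.

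**Holm at 480 completers.** The smaller p is tested at .025; if it is significant, the other is tested at .05. At correlation 0:
- 8b SD: .9207 + (.9546 − .9207) × .9444 = .953.
- Onset variability: .9444 + (.9695 − .9444) × .9207 = .968.
- Both: .8695 + .0320 + .0231 = .925.
- At least one: .9207 + .9444 − .8695 = .9956 under either rule, because the first step is the same.

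**Other correlations and inputs (bivariate normal).**

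| Completers | Onset effect | Correlation | Both, fixed split | Both, Holm | Only one, Holm |
|---|---|---|---|---|---|
| 480 | .35 | 0 | 87.0% | 92.5% | 7.1% |
| 480 | .35 | .5 | 88.3% | 93.0% | 5.2% |
| 480 | .35 | .8 | 89.9% | 93.7% | 2.9% |
| 480 | .45 | 0 | 91.7% | 95.3% | 4.7% |
| 600 | .35 | 0 | 94.7% | 97.3% | 2.6% |

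Over correlations 0 to .8 (480 completers, effect .35), Holm power is 95.3% down to 94.5% for 8b SD and 96.8% down to 95.8% for onset variability.

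**Error rate (1,000,000 draws per case).** With no effect on either endpoint, the family error is .050, .049, .047 and .040 at correlations 0, .3, .5 and .8. It is the same for both rules, since both make a first rejection at .025. With an effect on 8b SD only, Holm's false rejection rate for onset variability is at most .048.

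**The case against.** The strongest reply is that nothing in the plan fails. The split is valid, 560 reproduces, and power at 480 completers is already 92.1% and 94.4%. The gain is 2 to 3 points per endpoint, and the chance of at least one success does not move. All of that stands: this is lost efficiency, not an error.

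A reader might infer from the closing sentence of 14.8.1 that 90% joint power is promised and missed. The text does not support that. It sizes each endpoint separately and takes the larger number, so the claim is about each endpoint, and it is true. Even read jointly, the fixed split gives about 92% at effect size .45 and about 95% with 600 evaluable. It falls below 90% only at the low end of the effect range with attrition applied. The protocol sets no requirement that both primaries succeed.

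A reader might also see a contradiction in using Hochberg for the secondaries and a fixed split for the primaries. Both are legitimate, and one does not oblige the other.

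Two costs of Holm are real. Intervals matched to it are less simple than 97.5% intervals. And the freed .025 goes first to the other primary, so if only one primary succeeds no alpha is left for that intervention's secondaries. This happens in about 3–7% of trials at 480 completers. The second cost is partly there already: under the fixed split, one success could validly pass on only .025, while 10.4.3 tests the secondaries at .05 and does not say which primaries must be won.

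**Conclusion.** The concern holds as a point of efficiency. The fixed split meets its own target, but it buys no extra control of the .05 over the two endpoints and gives up power that Holm keeps. With 480 completers, SD 15, a 5-unit difference and onset effect .35, the gain is about 2.5 to 3 points for 8b SD, 1 to 2.5 points for onset variability, and about 4 to 5.5 points for winning both over correlations 0 to .8. At effect size .45 winning both rises from about 92% to 95%; with 600 evaluable at .35, from 94.7% to 97.3%. The attrition on the 600, equal allocation and the correlation are assumptions; the direction of the gain depends on none of them.

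The .05 here covers two endpoints for one intervention. It might seem natural to extend the step-down to all four tests, light and melatonin together. That widens error control but can cost power: if only one intervention works (480 completers, effect .35, correlation 0), 8b SD falls to 89.5% and winning both to about 83%, below the present 92.1% and 87.0%. The gains above belong only to Holm within each intervention.

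**What to change.** In 14.8.1, replace the fixed split with Holm within each intervention: test the smaller of the two primary p-values at two-sided .025 and, if it is significant, the other at two-sided .05. State there, with a matching line in 10.4.3, that Appendix B secondaries open as confirmatory at .05 only when both primaries for that intervention are rejected, and are otherwise exploratory. Carry the same wording into the SAP before unblinding.

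The change needs no added patients and no new assumption. Its cost is a few sentences, less simple confidence intervals for the primaries, and exploratory secondaries in the small share of trials where only one primary succeeds.

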14 APPENDIX B: COMPLEX PASC-RELATED SLEEP DISTURBANCES (CPSD)

14.1 STUDY DESIGN AND RATIONALE

The Complex PASC-Related Sleep Disturbances (CPSD) Appendix B combines brief education and a tailored sleep timing prescription for CPSD (referred to as RESET-PASC) with therapies that modify circadian timing for participants who report poor sleep quality or daytime sleep-related impairment. The intervention therapies involve tailored lighting (TL) and melatonin. Participants will be randomly assigned to one of four groups: (a) active TL + oral melatonin, (b) active TL + placebo melatonin, (c) placebo TL + oral melatonin, and (d) placebo TL + placebo melatonin. All groups will receive RESET-PASC. The 2x2 factorial design schema is shown in Figure 5. The intervention duration will be 9 weeks.

Figure 5. Appendix B 2x2 Factorial Design

		Pharmacologic Intervention						
_		Melatonin	Placebo					
imenta ention	Light	Melatonin + Light	Placebo + Light					
Environmental Intervention	Placebo Light	Melatonin + Placebo light	Placebo + Placebo light					
_	Reset-PASC							

PASC can lead to complex sleep disturbances that present similarly to but have overlapping qualities of known types of disturbed sleep, such as insomnia and circadian rhythm/sleep-wake disorders. Both types of sleep disturbances affect one's ability to sleep at night, and many patients with PASC present with symptoms of both insomnia and sleep-wake rhythm disturbances, suggesting common underlying mechanisms. Intervention strategies for the two conditions often overlap. Thus, the interventions in this study target common underlying mechanisms and represent the typical, real-world approaches for treating patients with complex sleep disturbances.

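### Appendix B's .025-per-endpoint split holds the error rate at .05 only per intervention, not overall, and its stated inputs do not yield the 600 participants it says are needed

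*Protocol*

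**What the plan says.** Section 14.1 describes two blinded interventions, tailored light and melatonin, each against its own placebo: "Participants will be randomly assigned to one of four groups". Section 14.8.1 confirms that "Complex PASC-related Sleep Disturbances is a 2X2 factorial design" and adds: "There will be two independent primary endpoints, namely (1) PROMIS 8b SD and (2) variability in sleep onset". It then states that "each endpoint will be tested at .025 type I error rate to maintain the overall error rate at .05".

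Two sample sizes follow. For PROMIS 8b, with assumptions carried over from Appendix A, "A total of 560 participants is needed to detect a 5-unit difference between groups with at least 90% power". For sleep onset variability, "a total sample size of 600 participants is needed", with at least 90% power for an effect size of .35 to .45, and with 70 minutes assumed in the control group and roughly 45 in the intervention group. The larger figure becomes the total for the appendix.

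Section 14.8.1 does not say which contrasts are the primary tests.

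**The concern.** A 2x2 factorial normally asks two questions of each endpoint: does light work, and does melatonin work? With two endpoints that makes four primary tests. Halving alpha once pays for the endpoints but not for the second intervention, so the claim about the overall rate looks too strong. It matters because section 10.4.3 opens formal testing of the secondary endpoints once the primary null hypothesis is rejected, so what counts as a primary rejection, and at what error rate, needs to be clear.

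The sample size text has two further gaps. It speaks of a difference between groups, while section 14.1 uses that word for the four cells, so a reader cannot tell which comparison has 90% power. And 600, which fixes the size of the trial, should be recoverable from the effect sizes, alpha and power given beside it.

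**Working it through.** **Inputs.** Two-sided testing (section 10.4.1: "All testing hypotheses and estimated confidence intervals will be two-sided at a .05 significance level"); alpha .025 per endpoint, 90% power and effect sizes .35 to .45 (14.8.1); a 5-unit difference with SD 15, and 20% attrition (13.7.1: "units (ie, an effect size of .33), two-sided type I error of .05"). Equal allocation to the four cells is assumed, since no ratio is given.

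**Formula.** Section 13.7.1 uses a treatment-effect variance of 4σ²/n, so the total evaluable is n = 4(z₁₋α/₂ + z.₉₀)²/d², divided by 0.8 for attrition.

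**Appendix A reproduces.** With α = .05 and d = 5/15: 36 × (1.960 + 1.282)² = 378.3, so 379; 379/0.8 = 473.75, so 474. Both match.

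**560 reproduces.** With α = .025: 36 × (2.241 + 1.282)² = 36 × 12.411 = 446.8; divided by 0.8 this is 558.5. Rounded up to equal halves, 448/0.8 = 560. So 560 compares one half of the trial with the other, which is a factor main effect with no interaction. At 600 with 20% attrition (480 evaluable), 8b power is Φ((1/3)√480/2 − 2.241) = 92%.

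**600 does not reproduce.** With α = .025:

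| d | Evaluable: 4 × 12.411/d² | With 20% attrition |
|---|---|---|
| .35 | 405.3 (406) | 506.6 (507) |
| .45 | 245.2 (246) | 306.4 (307) |

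Figures near 600 appear only under conditions the text does not state, such as d = .35 at α = .0125 with attrition (583), or a rank-test efficiency of .864 at d = .35 with attrition (586).

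What 600 does deliver, with 480 evaluable:
- Effect size detectable with 90% power: 2 × 3.523/√480 = .32.
- Power at d = .35: 94%. At d = .45: 99.6%.
- Alternatively, 90% power at d = .35 with a loss of 1 − 405.3/600, about 32%.

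**The minutes.** Section 10.4.3 defines the tracker measure as a within-person standard deviation. If 70 and 45 are typical values of that measure, the difference is 25 minutes, and d of .35 to .45 implies a between-person SD of 25/.45 = 56 to 25/.35 = 71 minutes. That SD is not given.

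**Error rate.** Within one intervention (two tests at .025, independent): 1 − .975² = .0494. Across four tests: 1 − .975⁴ = .0963. The two main effects are independent in a balanced 2x2, so correlation enters only through the endpoints: the four-test rate is .094 at correlation .3 and .091 at .5. The upper bound is .10.

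**Alternatives, by simulation** (480 evaluable, endpoint correlation .3):
- Holm over the two endpoints within each intervention: 8b power stays at 92% if sleep onset is unaffected and rises to 95% if it is affected too. The error bound is unchanged.
- Holm over all four tests at .05: 8b power is about 88% to 89% if one intervention works, and about 95% if both work on both endpoints.

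**The case against.** The best defence of the error claim is that each factor of a factorial trial is a separate question, so .05 per factor is enough. That is a common and respectable position, and the plan meets it (.0494). The protocol also lists no contrasts, so four tests is an inference from the design, and the detail may be left to the SAP. What remains is that the protocol itself claims an overall rate, without restricting it to one intervention.

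On 600, the defence is that section 14.8.1 carries over Appendix A's assumptions explicitly only for 8b. Section 10.4.1 drops anyone missing either sleep onset measurement, so a tracker loss above 20% is plausible, and about 32% would give 600. This stands: 600 is undocumented rather than shown to be wrong, and it errs on the large side.

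A reader might go further and infer that the trial falls well short of 90% power, by taking the groups to be single cells compared with one another. The protocol does not support that. It proposes no cell-versus-cell test, section 14.8.1 speaks of one control and one intervention group, and 560 reproduces as a main effect. That reading would also be inconsistent with counting four tests, which presumes main effects.

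**Conclusion.** The point stands on the stated error rate and on the derivation of the sample size, not on power. If both main effects are primary on both endpoints, .05 holds per intervention, and the chance of at least one false primary claim across the appendix is about .091 to .096. The 560 is right for a main effect, given no interaction and 20% attrition, but the text does not identify that contrast. The 600 does not follow from the inputs beside it, which give 307 to 507 at 20% attrition. The statement of at least 90% power is nevertheless true at 600 for main effects on both endpoints.

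A reader might also conclude that the total should be cut to 560. The documents do not justify that: it would remove the margin against tracker loss, for which no rate is stated. These results assume equal allocation, no interaction and, for sleep onset, the 20% attrition borrowed from Appendix A.

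**What to change.** Revise section 14.8.1, and correct its heading, which refers to dose selection.

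1. Name the two factor main effects as the primary contrasts and state that power assumes no interaction.
2. Choose the scope of error control and say so. Either (a) claim .05 per intervention and replace the fixed .025 by Holm over the two endpoints within each intervention: same error bound, never less powerful, 8b power 92% to 95%. Or (b) if .05 across all four tests is intended, use Holm over the four and restate 8b power at 600 as about 88% to 89% if one intervention works and about 95% if both do, against 92% now.
3. Keep 600 and state what it delivers: an effect size of about .32 at 20% loss, or .35 at about 32% missing tracker data. Give the between-person SD behind the 70 versus 45 minute assumption.

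No participants are added. Option (a) costs only wording. Option (b) costs about 3 to 4 points of 8b power when one intervention works, so the promise of at least 90% for both endpoints would have to be qualified.
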